### **5.2.1 Sensitivity analyses**

We do not anticipate strong cluster-level effects; however, we will conduct a sensitivity analysis including rehabilitation group in the mixed linear model with follow-up timepoints as level 1, participants as level 2, and rehabilitation group as level 3.

### **5.2.2 Subgroup analyses and treatment effect heterogeneity**

If the data material allows it, we will explore whether age, anxiety and/or depression, pain intensity, level of physical activity, and specific combinations of insomnia symptoms at baseline moderate the effect of dCBT-I on primary outcomes. Each of these demographics and characteristics will be categorized into 2 or 3 categories based on examination of the dataset without randomization allocation information.

Decision whether the data material allows what is mentioned above will be conducted before the group information is revealed.

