### **1.3.2 Secondary and exploratory objectives**

Secondary objectives:

- 1) Examine the difference in the proportion of participants that achieves an 8-point improvement in their ISI-score between inpatient multidisciplinary rehabilitation + dCBT-I (intervention group) and inpatient multidisciplinary rehabilitation only (control group), 3-, 6-, and 12 months after end of rehabilitation.
- 2) Evaluate the effectiveness of the intervention on pain intensity, fatigue, health-related quality of life, physical function, and physical activity at 3-, 6-, and 12 months after end of rehabilitation.
- 3) Evaluate the long-term effectiveness of the intervention on sickness absence and use of prescribed sleep and pain medication during 12 months of follow-up after rehabilitation (this will be done if successful register linkage within the time frame of the project).

If the data material allows it, it will be relevant to examine the following exploratory objectives:

- 4) Explore whether changes in pain intensity and fatigue mediate the effect of dCBT-I on insomnia severity.
- 5) Explore whether sex, age, symptoms of anxiety and depression, pain intensity and level of physical activity at baseline moderate the effect of dCBT-I on insomnia severity and secondary outcomes (pain intensity, health-related quality of life, sickness absence and use of prescription sleep and pain medication).

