### 2.3 Determination of sample size

We anticipated that around five of 10 patients will have insomnia within each rehabilitation group and that the average Insomnia Severity Index (ISI)-score for participants completing usual treatment will be 15 ( $SD = 4$ ). An average 4-point improvement on the ISI score is considered a meaningful change. In order to maximize the number of participants receiving the additional treatment (dCBT-I), we will randomize the participants to the intervention and usual care at a ratio of 2:1. Recruiting 15 clusters with 2:1 randomization will achieve 80% power to detect a 4-point difference between the intervention and usual treatment group, with a conservative assumption that the intraclass correlation is 0.2 and the coefficient of variation in cluster size up to 0.7, and with a significance level of 5%. This would mean that around 150 participants will be screened to give an expected sample size of 75 (50 in dCBT-I + usual care and 25 in usual care). We expect a dropout rate of approximately 20% and that around 50% of the participants in the intervention group will complete at least four of the dCBT-I modules. Given that the per-protocol analysis is of particular interest in this study, we aim to recruit 21 clusters to account for the fact that we expect an average of four participants per cluster in the control group to complete the follow-up, and an average of two participants in the intervention group to complete at least four of the modules and attend the follow-up.

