#### 5.1.2 Secondary outcomes

- 1) Difference in the proportion of participants that achieves an 8-point improvement on ISI between the intervention group and the control group. This is in accordance with the literature suggesting an improvement of the ISI score  $\geq 8$  points is a meaningful improvement, indicating that the intervention has a positive impact on the individual’s sleep [2].
- 2) The effect of the intervention on
  - a. pain intensity measured using a visual analogue scale from 0 to 100.
  - b. fatigue measured using a visual analogue scale from 0 to 100.
  - c. health-related quality of life measured by EQ-5D.
  - d. physical function measured by PSFS.
  - e. physical activity measured by three questions about frequency, duration and intensity of physical activity per week

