## **5.2 Analysis of primary outcome**

We will use linear mixed model analysis to estimate mean difference in ISI between the two groups at 3, 6 and 12 months of follow-up, with the primary outcome measurement at 3 months. The model will include participant ID as a random effect and time, time–group interaction and baseline covariates as fixed effects. Of baseline covariates we will include age, sex, and education. Determination of possible categorizing of the covariates will be done before unblinding and published in an updated version of this SAP.

The assumption of normally distributed residuals will be assessed by visual inspection of histograms and Normal Q-Q plots. Model assumptions for mixed models will be checked: residuals (approximately) normally distributed and homogeneity of residual variance (homoscedasticity).

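### Minor: the moderator analyses will cut age, HSCL-25 and pain scores into 2 or 3 groups at cut points not yet fixed, which wastes information in interaction tests that are already weak

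*SAP*

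**What the plan says.** Section 5.2.2 lists five candidate moderators for the primary outcome: "we will explore whether age, anxiety and/or depression, pain intensity, level of physical activity, and specific combinations of insomnia symptoms at baseline moderate the effect". It then fixes how they will be handled: "Each of these demographics and characteristics will be categorized into 2 or 3 categories based on examination of the dataset without randomization allocation information". This is worded as a commitment for every moderator. No cut points, no rule for finding them and no continuous analysis are given.

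At least three of the five are numeric. Age is one. Anxiety and depression are measured with the HSCL-25 (Table 1, section 2.7.2). The third is "pain intensity measured using a visual analogue scale from 0 to 100" (section 5.1.2). The other two differ: combinations of insomnia symptoms are naturally categorical, and activity is "physical activity measured by three questions about frequency, duration and intensity of physical activity per week", with no scoring stated.

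The status of the work is clear. Section 1.3.2 introduces moderation with "If the data material allows it, it will be relevant to examine the following exploratory objectives". Section 5.2.2 repeats the condition and says the decision will be taken before group information is revealed.

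**The concern.** Cutting a numeric score treats all patients within a category as alike and assumes that the treatment effect jumps at the cut. If the effect changes gradually with the score, the test loses power. Because the cuts will come from this sample, a finding about, say, a high-pain group carries over to another cohort only if the same cut is used there.

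The question at stake is who benefits from dCBT-I. The trial is small for that question, and categorising makes it likelier that a real gradient is reported as no moderation.

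**Working it through.** **1. The plan's own power figure.** Section 2.3 says: "Recruiting 15 clusters with 2:1 randomization will achieve 80% power to detect a 4-point difference between the intervention and usual treatment group". Its inputs are SD 4, ICC 0.2, coefficient of variation (CV) of cluster size 0.7, two-sided 5%, and 75 participants (50:25), hence m = 5 per cluster.

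- L = m·ICC/(m·ICC + 1 − ICC) = 1/1.8 = 0.556
- Design effect = [1 + (m − 1)·ICC]/[1 − CV²·L·(1 − L)] = 1.8/(1 − 0.49 × 0.556 × 0.444) = 2.048
- Effective control n = 25/2.048 = 12.2; SE = 4 × √(1.5/12.2) = 1.40
- Power = Φ(4/1.40 − 1.96) = 81.4%

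The stated 80% is reproduced. A simpler design effect of 2.29 gives 77.0%, and ignoring CV (1.8) gives 86.1%. The SAP states no power for any interaction.

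**2. Information kept after grouping.** Assume a standard normal moderator and a linear interaction. The share kept is Σ pₖ·(mean of group k)².

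- Median split: group means ±0.798, so 0.798² = 2/π = 0.637 is kept and 36% is lost.
- Equal tertiles scored as a trend: outer means ±1.091, so (2/3) × 1.091² = 0.793 is kept and 21% is lost.

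The SAP fixes neither equal groups nor a distribution, so these two values are not bounds:

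| Assumption | Loss |
|---|---|
| Normal, two groups 33/67 | 41% |
| Normal, two groups 25/75 | 46% |
| Normal, two groups 20/80 | 51% |
| Normal, three groups 27/46/27 | 19% |
| Normal, three groups 10/80/10 | 38% |
| Uniform, equal groups, two / three | 25% / 11% |
| Exponential, equal groups, two / three | 52% / 35% |

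**3. Effect on power.** The recruitment target is 21 clusters. With 5 per cluster and 20% dropout, 21 × 5 × 0.8 = 84 are followed, or 56:28 at 2:1.

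*No clustering.* Residual SD 4, normal moderator, F-test of the interaction, 6,000 simulated trials per cell:

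| Effect change per moderator SD | Continuous | Median split | Tertiles, 2 df |
|---|---|---|---|
| 2.5 ISI points | 73% | 51% | 50% |
| 2 ISI points | 54% | 37% | 35% |

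*With the SAP's clustering inputs.* Take an interaction as large as the design effect: a 4-point difference in treatment effect between the lower and upper halves. The slope is 4/(2 × 0.798) = 2.51 points per SD, almost the same as the 2.5 above.

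- Main-effect SE = 4 × √(1.5 × 2.048/28) = 1.325
- Continuous: Φ(2.51/1.325 − 1.96) = 47%
- Median split: SE of the contrast is 2 × 1.325, so Φ(4/2.65 − 1.96) = 33%
- Tertile trend: Φ(√0.793 × 2.51/1.325 − 1.96) = 39%
- Tertiles, 2 df: 31% (non-central chi-square)

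Applying the full design effect is pessimistic for a patient-level moderator, because much of its variation lies within rehabilitation groups. The unclustered table is the more favourable case.

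The 21% tertile loss belongs to the trend test. The 2-df test also spends a degree of freedom, so its power should not be paired with that 21%.

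**The case against.** The strongest reply is that nothing confirmatory depends on this. Moderation is exploratory, done only if the data allow, and section 1.1 says that exploratory analyses are not described in detail. That stands, and it makes the point minor.

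The figures also favour continuous modelling, because they assume a linear interaction; a true threshold effect would favour categories. The interactions assumed are large: at 2.5 points per SD, the effect changes by 5 points between patients one SD below and one SD above the mean. At 1 point per SD (56:28, no clustering, normal approximation), SE = 4 × √(1.5/28) = 0.926, and power is about 19% continuous and 14% with a median split, so neither analysis would be informative. This stands too. It limits what the change can achieve but gives no reason to discard information.

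Three stronger readings are not supported:

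- *Data-chosen cuts inflate false positives.* Cuts chosen without allocation information cannot be tuned to the treatment effect.
- *All five moderators are mishandled.* Symptom combinations are categorical, and activity may be.
- *The primary model will also categorise age.* Section 5.2 says only "Determination of possible categorizing of the covariates will be done before unblinding", calls such categorising possible, and promises publication in an updated SAP. That decision has not been taken.

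**Conclusion.** The point holds as a minor, cheap improvement. Section 5.2.2 commits to grouping three numeric scores at cut points still to be read from the sample, with no continuous analysis.

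For a normal moderator, a linear interaction and equal groups, the loss is about 36% (median split) or 21% (tertile trend). Across the other cases examined it runs from about 11% to just over 50%. For an interaction of about 4 ISI points between halves, grouping lowers power from about 73% to 50–51% without clustering (median split or 2-df tertiles). With the full design effect, it falls from about 47% to 31–39%, depending on the grouping and test. All of these are assumptions; none is a figure from the SAP.

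A reader might infer a threat to the trial's main conclusion. The documents do not support that: the primary and secondary treatment effects do not use these categories.

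**What to change.** Amend the sentence in section 5.2.2 as follows:

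- Age, HSCL-25 score and pain intensity enter the mixed model as continuous moderator-by-group-by-time interactions.
- Linearity is checked by a plot or a restricted cubic spline.
- For these three, categories serve only to display estimated effects at chosen values.
- Allocation-blind categories are kept for insomnia-symptom combinations and, if it is not scored continuously, for physical activity.

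The cost is one amended sentence and one changed model term. It can go into the updated SAP that section 5.2 already foresees. The downside is a linearity assumption that must be checked and a slightly less simple results table.

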## STATISTICAL ANALYSIS PLAN for “Digital sleep therapy in patients with Musculoskeletal complaints and insomnia”

### 5.2.3 Missing data

We will use the linear mixed model analyses, which provides unbiased effect estimates under the assumption that the outcome data is missing at random.

## 5.3 Analysis of secondary outcomes

For binary secondary outcomes (e.g., clinically relevant change in ISI, minimal important change in PSFS), we will use a generalized estimated equation logistic model to estimate the odds ratio (OR) for achieving at least an 8-point improvement in ISI score. In these analyses, we will assume an exchangeable correlation structure and a robust variance estimator. For the other secondary outcomes, a mixed linear regression model will be used.

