### **3.3 Analysis populations**

#### **3.3.1 Intention to Treat (or Full Analysis Set)**

Effect analyses of primary and secondary outcomes will be performed after the intention-to-treat (ITT) principle, i.e., we will include all participants that were included and randomized.

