### 4.2 Withdrawal / follow-up

We will describe how many participants drop out during the study and reason for this if available (due to ethical consent there is no obligation for provide a reason for dropping out). If participants do not answer the questionnaire, they will be registered as ‘lost to follow-up’. If participants withdraw their consent, they will be excluded unless their data has already been included in analyses or published.

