## **STATISTICAL ANALYSIS PLAN for “Digital sleep therapy in patients with Musculoskeletal complaints and insomnia”**

The above listed outcomes will be analyzed for 3-, 6-, and 12 months of follow-up, with 3 months being the main assessment point.

In additional publications, we will investigate the long-term effects (12 months) of dCBT-I on sickness absence and use of prescribed sleep and pain medication.

- 1) Work outcomes: 1) Difference between the two groups in total number of sickness absence during 12 months of follow-up and 2) probability of working (i.e., not receiving medical benefits) each month during 12 months of follow-up. Based on registry data from NAV.
- 2) Difference in the proportion of participants that obtain prescriptions for sleep and pain medication between two groups during 12 months of follow-up. Based on registry data from NPD.

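### The GEE planned for the ISI and PSFS responder outcomes does not share the missing-at-random validity that the SAP claims for its mixed model, and no missing-data rule covers it

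*SAP*

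**What the plan says.** Section 5.1.2 lists this outcome first among the secondary outcomes: "Difference in the proportion of participants that achieves an 8-point improvement on ISI between the intervention group and the control group". On timing it adds: "The above listed outcomes will be analyzed for 3-, 6-, and 12 months of follow-up, with 3 months being the main assessment point". Section 5.3 gives the method: "we will use a generalized estimated equation logistic model to estimate the odds ratio (OR) for achieving at least an 8-point improvement in ISI score", and "we will assume an exchangeable correlation structure and a robust variance estimator". It names minimal important change in PSFS as another outcome of the same type. It states no covariates, weights, imputation, non-responder rule or missingness assumption.

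The SAP's only missing-data rule is section 5.2.3, under the primary outcome: "We will use the linear mixed model analyses, which provides unbiased effect estimates under the assumption that the outcome data is missing at random". On unanswered questionnaires, section 4.2 says "If participants do not answer the questionnaire, they will be registered as" lost to follow-up, and assigns no value. For primary and secondary outcomes alike, section 3.3.1 says "we will include all participants that were included and randomized". Section 2.3 says "We expect a dropout rate of approximately 20" per cent. Table 1 shows that ISI and PSFS are collected at baseline and at the end of rehabilitation as well as at 3, 6 and 12 months.

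**The concern.** The assurance in section 5.2.3 rests on likelihood estimation. A GEE solves estimating equations on the responses that were observed, so it does not share that property. If people stop answering because of how their insomnia had developed by an earlier visit, dropout is missing at random given the recorded scores, but the observed responders are still a selected sample. The robust variance corrects the standard errors and leaves this bias in place.

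This goes beyond a missing detail. The SAP allows dropout to depend on observed data for the continuous ISI score, then assigns the same score, dichotomised, to a method that can fail in that situation. At stake are the responder proportions, their difference and, in some circumstances, the odds ratio. A further risk is that about one in five participants would be handled by software default or by a decision taken late.

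**Working it through.** **The plan's own figure.** The SAP gives no figure for the responder outcome. Its 80% power refers to the 4-point mean difference. It reproduces at 81.4% under a normal approximation with a design effect of 2.05 for unequal clusters. Other approximations differ, and nothing below depends on it.

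**Inputs.** From section 2.3: usual-care ISI 15, SD 4, a 4-point effect (so app mean 11), 20% dropout, and 50 versus 25 participants. Assumed, because the SAP does not give them: baseline mean 18, the correlations between visits, the end-of-rehabilitation means, and how strongly dropout depends on early change.

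**Step 1, response without dropout.** Response means baseline minus 3-month ISI of at least 8. The change has SD = 4 × √(2(1 − ρ)), with mean 3 (control) or 7 (app).
- ρ = 0.5: SD 4.00. Control P(Z ≥ 5/4.00) = 0.106, app P(Z ≥ 1/4.00) = 0.401. OR = (0.401/0.599)/(0.106/0.894), about 5.7.
- ρ = 0.65: SD 3.35. Control 0.068, app 0.383, OR about 8.6.

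**Step 2, the planned type of GEE under dropout.** A large simulated sample (150,000 participants, 2:1) was fitted with an exchangeable logistic GEE with time and time-by-arm terms. Correlations between visits were 0.35 to 0.7, with end-of-rehabilitation means of 15.5 (control) and 13 (app). In each arm 20% dropped out before 3 months, depending on the change already observed at the end of rehabilitation.

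| Dropout mechanism | Control share | App share | Difference | 3-month OR |
|---|---|---|---|---|
| None (full data) | 0.119 | 0.404 | 0.285 | 5.04 |
| Completely at random | 0.118 | 0.404 | 0.286 | 5.08 |
| Poor early responders leave, both arms | 0.140 | 0.455 | 0.315 | 5.13 |
| Poor early responders leave, app arm only | 0.118 | 0.455 | 0.337 | 6.25 |
| Same, stronger dependence | 0.118 | 0.475 | 0.357 | 6.79 |
| Good early responders leave, app arm only | 0.118 | 0.347 | 0.229 | 3.98 |
| Good leave control, poor leave app | 0.082 | 0.455 | 0.373 | 9.33 |

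The difference shifts by +3.0 points with the same mechanism in both arms, by +5.2 or −5.6 with dropout that depends on early change in the app arm only, by +7.2 with stronger dependence, and by +8.8 in the opposed case.

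**Step 3, a milder set of assumptions.** Using the correlations of step 1, and odds of dropout multiplied by 2.2 to 4.1 per SD of non-improvement in the app arm only, the OR is 6.3 to 6.7 instead of 5.7 (ρ = 0.5), or 9.6 to 10.1 instead of 8.6 (ρ = 0.65). The difference is overstated by 3 to 4 points. With the mechanism in both arms the OR hardly moves and the difference is overstated by about 2 to 3 points.

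**Step 4, comparison with sampling error.** Completers: 0.8 × 50 = 40 and 0.8 × 25 = 20. At ρ = 0.5, SE(log OR) = √[1/(40 × 0.401) + 1/(40 × 0.599) + 1/(20 × 0.106) + 1/(20 × 0.894)], about 0.80 before any allowance for clustering. The step 3 bias at ρ = 0.5 is ln(6.3/5.7) = 0.10 to ln(6.7/5.7) = 0.16, so 0.1 to 0.2 SE. With the step 2 shares the SE is about 0.76. The biases are then ln(6.25/5.04) = 0.22 (0.3 SE), ln(6.79/5.04) = 0.30 (0.4 SE), ln(3.98/5.04) = −0.24 (−0.3 SE) and, in the opposed case, ln(9.33/5.04) = 0.62 (0.8 SE). The SE of the difference in proportions is about 10 points.

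**Step 5, bounds without a dropout model.** Suppose observed response is 20% versus 40% (assumed), with 20% missing per arm. The observed OR is 2.67. Counting all missing as non-responders gives 0.16 versus 0.32, OR 2.47. The extremes are 0.36 versus 0.32 (OR 0.84) and 0.16 versus 0.52 (OR 5.69).

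**The case against.** Four points can be made for the plan.

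1. A reader might infer that the GEE is valid only under completely random dropout. That is too strict, since it also tolerates dropout that depends only on covariates in the model, such as arm and visit. This stands. It does not rescue the analysis, because section 5.3 lists no covariates, and the age, sex and education of section 5.2 would not stand in for earlier ISI.

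2. A reader might infer that the primary analysis is clearly safer because it uses the end-of-rehabilitation ISI of people who leave early. The SAP does not establish this. Section 5.2 speaks of 3, 6 and 12 months and does not say whether that visit enters the model. The mismatch that can be shown is with the property claimed in section 5.2.3.

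3. A reader might infer that the odds ratio will be inflated in favour of the app. The SAP does not support that either. With the same mechanism in both arms the OR barely moves, and with arm-specific mechanisms it can move either way. Sections 1.3.2 and 5.1.2, however, frame the outcome as a difference in proportions, and that shifts even when the mechanism is common to both arms.

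4. The size rests on inputs outside the SAP, sampling error dominates, the outcome is secondary, and a rich imputation model would be fragile. All of this stands. It limits the importance of the point and shapes the fix.

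**Conclusion.** The point holds as a should-fix for secondary outcomes. Followed as written, section 5.3 gives the ISI and PSFS responder analyses a method that is unbiased only if dropout is completely at random or explained by covariates in the GEE. It also leaves out participants with no follow-up score despite the intention-to-treat statement. That no weighting or imputation is used is read from the SAP's silence, but it is what the stated model does by default.

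Under the illustrative assumptions, 20% dropout that depends on early change biases the difference in responder proportions by about 2 to 5 points in the plainer scenarios, and by up to about 9 when the arms have opposed mechanisms. The OR is materially affected only if the mechanism differs by arm, in either direction. In most scenarios the bias is 0.1 to 0.4 standard errors, so it would seldom change a conclusion by itself. The continuous outcomes, analysed by mixed models, are outside this point.

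**What to change.** In section 5.3, state that the continuous ISI and PSFS scores will be multiply imputed before they are dichotomised. The imputation would use arm, baseline, end-of-rehabilitation and other observed scores, age, sex and education. Derive responder status from the imputed scores, fit the planned GEE in each imputed set and pool. Keep the observed-data GEE as a sensitivity analysis. Extend section 5.2.3 to cover the binary outcomes and state the assumption made for them.

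Keep the imputation model parsimonious. Section 2.3 aims for 21 clusters at 2:1, which is about 7 control clusters, and at four completers each about 28 control completers. Rehabilitation group should be accounted for only as far as those numbers allow.

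The cost is SAP wording and some extra Stata syntax, with no new data. The downside is that a small imputation model must be specified before unblinding, and it may be unstable in the control arm if made too rich. Section 5.2 already foresees an updated SAP before unblinding, and section 3.4.2 foresees syntax published before the main analyses, so there is a place to put it.

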#### **Questionnaires**

Self-reported web-based questionnaires are answered at five time points: at baseline (prior to randomization), 6 weeks (at the end of rehabilitation), at 3 months (primary outcome measurement), 6 months, and 12 months after end of rehabilitation.

In addition, diagnoses and use of medication at baseline will be available through the electronic patient records.

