## 5. Analysis

### 5.1 Outcome definitions

#### 5.1.1 Primary outcome

The primary outcome is insomnia measured by ISI at three months follow-up. ISI is the gold standard self-report measure of insomnia severity in clinical practice, consisting of seven items assessing symptoms of insomnia such as difficulty falling or staying asleep, satisfaction with sleep, and degree of impairment with daytime functioning. The total score of ISI ranges from 0 to 28. ISI has been validated and has proven sensitive to therapeutic changes [2]. For the primary analyses ISI will be included as a continuous variable. See table in 2.7.2 for details concerning measurement time.

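### The GEE for the 8-point ISI responder outcome names no covariate and so leaves out baseline ISI; a chance baseline imbalance then shifts the comparison towards the arm that starts worse

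*SAP*

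**What the plan says.** SAP section 5.1.2 lists as the first secondary outcome the "Difference in the proportion of participants that achieves an 8-point improvement on ISI between the intervention group and the control group"; section 1.3.2 has the same objective at 3, 6 and 12 months. Both describe a change from each participant's own starting score.

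Section 5.3 gives the model as a "generalized estimated equation logistic model to estimate the odds ratio (OR) for achieving at least an 8-point improvement in ISI score" and adds only: "In these analyses, we will assume an exchangeable correlation structure and a robust variance estimator". It lists no covariates, and no group or time terms either.

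The SAP's one covariate list belongs to the primary mixed model in section 5.2: "Of baseline covariates we will include age, sex, and education". Carrying that list over to section 5.3 would still leave baseline ISI out.

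Baseline ISI is available. Section 2.7.1 has questionnaires completed "at baseline (prior to randomization), 6 weeks (at the end of rehabilitation), at 3 months (primary outcome measurement" and later, and Table 1 marks ISI at baseline and every later visit.

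**The concern.** Defining an outcome as a change does not adjust it for baseline. Unless baseline and follow-up move together one for one, a participant who starts high tends to fall further, and one who starts low has little room to fall 8 points. On the ISI ("The total score of ISI ranges from 0 to 28") anyone starting below 8 cannot respond at all. Baseline ISI is therefore likely to be the strongest available predictor of responder status.

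Whole rehabilitation groups are randomised 2:1, and 21 are planned, so about 14 versus 7. With so few units, some difference between the arms in mean baseline ISI is to be expected. In an unadjusted responder analysis it favours the arm with the worse starting insomnia. An unadjusted comparison of follow-up scores would be pushed the other way. The responder result could then disagree with a baseline-adjusted mean difference on the same scale for that reason alone.

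**Working it through.** **Inputs from the SAP (section 2.3 unless noted).** Usual-care ISI mean 15, SD 4; difference 4 points; ICC 0.2; coefficient of variation of cluster size 0.7; 2:1 allocation; 15 clusters for power and 21 to be recruited; about 5 participants per cluster and about 4 followed up; response is a fall of at least 8 points (section 5.1.2).

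**Assumed, because the SAP does not give them.** Baseline mean 17-19, baseline SD (s0) 3-4, baseline to follow-up correlation (r) 0.3-0.5.

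**1. The plan's own figure.** Section 2.3 says that 15 clusters "will achieve 80% power to detect a 4-point difference between the intervention and usual treatment group". Take m = 5 and L = 5/(5 + 0.8/0.2) = 0.556. The design effect is [1 + 4 × 0.2]/[1 - 0.49 × 0.556 × 0.444] = 1.8/0.879 = 2.05. Effective controls are 25/2.05 = 12.2, and the SE is 4 × √(1/12.2 + 1/24.4) = 1.40. Then 4/1.40 - 1.96 = 0.89, which gives 81% power, so the stated 80% is reproduced. It concerns continuous ISI; no figure is given for responders. A cruder formula, 1 + [(1 + 0.49) × 5 - 1] × 0.2, gives a design effect of 2.29.

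**2. How large a chance imbalance is.** 21 groups of 5 give about 70 v 35. With baseline SD 4, the SE of the difference in mean baseline ISI is 4 × √(1/70 + 1/35) = 0.83 if participants are independent. If the ICC and size variation also apply at baseline it is 0.83 × √2.05 = 1.19 to 0.83 × √2.29 = 1.25. With SD 3 these fall by a quarter, to about 0.62-0.94. A 1-point imbalance is an ordinary event.

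**3. What 1 point does (normal model).** Let D be the fall in ISI.
- One extra baseline point raises expected D by b = 1 - r × 4/s0.
- SD(D) = √(s0² + 16 - 8 × r × s0).
- P(response) = 1 - Φ((8 - mean D)/SD(D)).
- The share of the variance of D explained by baseline is b² × s0²/SD(D)².

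With baseline mean 17 and no treatment effect, mean D = 17 - 15 = 2, or 2 + b in an arm that starts 1 point higher:

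| s0 | r | b | SD(D) | share | P(response) | P, starting 1 point higher | shift |
|---|---|---|---|---|---|---|---|
| 4 | 0.3 | 0.70 | 4.73 | 35% | 10.2% | 13.1% | 2.9 points |
| 4 | 0.5 | 0.50 | 4.00 | 25% | 6.7% | 8.5% | 1.8 points |
| 3 | 0.3 | 0.60 | 4.22 | 18% | 7.7% | 10.0% | 2.3 points |
| 3 | 0.5 | 0.33 | 3.61 | 8% | 4.8% | 5.8% | 1.0 point |

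In the first two rows the spurious odds ratios are 1.33 and 1.29.

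**4. Simulation of the 3-month visit.** Set-up: 14 v 7 clusters, mean size 4, size CV 0.7, ICC 0.2, baseline ICC 0.1, true difference 0 or 4, baseline inputs as above.
- Unadjusted, each 1-point imbalance moves the responder difference by 0.9-4.7 percentage points. With baseline ISI in a logistic model and standardised proportions, the shift is about 1 point or less.
- Variance of the adjusted difference relative to the raw one is 0.80-1.06 with baseline ISI alone. The gain reaches about 20% at baseline SD 4. At SD 3 it runs from none, or a slight loss, to about 10%.
- Adding age, sex and education as well, treated as non-prognostic, gives a ratio of 0.84-1.28.

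**5. Why extra terms can cost precision.** Followed-up controls number about 7 × 4 = 28. At the first two response rates in the table, 28 × 0.102 = 2.9 and 28 × 0.067 = 1.9 control responders are expected. Over the full range of assumptions, with whole-number scores, the figure is about 2-6.

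**The case against.** **No bias.** A reader might infer that the planned responder analysis is biased. It is not: under randomisation both estimates are unbiased on average, and a valid interval already covers chance imbalance. The shift is also modest beside sampling error. In one scenario (baseline mean 19, SD 4, r 0.5, baseline ICC 0.2, true difference 4) one SD of imbalance moves the difference by 1.29 × 4.1 = 5.3 percentage points, against a sampling SD of 12.4. This stands and limits the point to precision and protection against imbalance.

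**Silence is not refusal.** A reader might infer that the SAP rejects adjustment. Section 5.3 simply does not say. However, the SAP presents itself in section 1 as the more detailed account of the analysis. The promised update (section 5.2) concerns only how covariates are categorised. The syntax to be published beforehand (section 3.4.2) is for the main analyses. Neither settles the matter.

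**The primary analysis.** A reader might infer that it too ignores baseline ISI. The SAP does not support that. The mixed model in section 5.2 lists time and time-by-group terms. If baseline is one of its repeated outcomes, which is not stated, baseline ISI is used there. That route is not open to a binary change outcome.

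**The gain rests on assumed inputs.** This also stands. The insomnia entry requirement may narrow the baseline SD, and at SD 3 there may be nothing to gain. With few responders, a long covariate list can do harm.

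**Conclusion.** The point holds in a limited form. As written, section 5.3 leaves out a strong predictor of response that is already collected, and borrowing the section 5.2 list would not put it in. The result is exposure to chance imbalance of about 1-5 percentage points in the responder difference per point of baseline ISI, towards the arm that starts worse. There is no bias on average. A gain in precision is likely if the baseline SD is near 4 and uncertain if it is near 3.

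The direction requires r × (follow-up SD)/(baseline SD) to be below 1, which is true throughout the range examined. The sizes depend on a baseline mean, SD and correlation that the SAP does not state. The outcome is secondary, so this does not threaten the trial's main conclusion. It is worth correcting because the remedy is cheap and because the covariate choice should be fixed before allocation is revealed.

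**What to change.** In section 5.3, state that the responder GEE includes group, time, time-by-group and baseline ISI as one continuous covariate. State also that model-standardised responder proportions by arm, and their difference with a 95% confidence interval, will be reported at 3, 6 and 12 months. That gives the difference in proportions that sections 1.3.2 and 5.1.2 define, which an odds ratio alone does not.

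Do not add age, sex and education to this model: with about 2-6 control responders expected, the extra terms can cost more precision than they return. State beforehand what will be reported if responders are too few for the model to fit; in simulations on similar assumptions, the control arm had no responder in up to 21% of runs.

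**Cost.** A sentence or two in the SAP and one covariate in the syntax, with no new data. The adjusted odds ratio becomes conditional on baseline and is not comparable with an unadjusted one. In a simulation of 70 v 35 independent participants (baseline mean 17, SD 4, r 0.3, true difference 4) the mean log odds ratio went from 1.57 to 1.96 on adjustment, and its mean SE from 0.66 to 0.75. Leading with standardised proportions avoids that confusion. With very few responders the gain may vanish or become a slight loss.
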